Risks associated with the use of adalimumab are well characterized, and are described in approved local product information. Adalimumab is associated with an increased risk for developing serious infections that may lead to hospitalization or death. Opportunistic infections due to bacterial, mycobacterial, invasive fungal, viral, parasitic, or other opportunistic pathogens have been reported with TNF α inhibitors. Reactivation of latent TB has been reported. All subjects will be tested for TB before study start as outlined in the exclusion criteria and will be carefully monitored for signs and symptoms of infection during and after the study. Study drug will be discontinued for serious infections as outlined in section 3.5. An increase of non-melanoma skin cancers, hematologic cancers and a potential increase of other cancers has been reported with use of TNF α inhibitors. Subjects will undergo regular assessments, including physical examination and haematological assessments.

TNF α inhibitors are commonly used as first line therapy in MTX-IR RA patients. Their efficacy in this patient population has been well established. Overall, the benefit of using adalimumab as proposed in this study is considered to outweigh any associated risks.

An independent data monitoring committee (DMC) appointed to monitor the study (with an interim safety analysis after the first 100 subjects complete 12 weeks of treatment) will provide an additional level of risk mitigation.

The overall risk:benefit balance of this study is considered favorable. For additional information about the risks of filgotinib, reference is made to the investigator brochure.

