3.5. Criteria for Interruption or Discontinuation of Study Treatment

3.5.1. Study drug interruption considerations:

The Gilead Medical Monitor should be consulted prior to study drug interruption when medically feasible.

Study drug interruption should be considered in the following circumstances; *prior to resumption of study drug, the investigator should discuss the case with the Gilead medical monitor:*

- Intercurrent illness that would, in the judgment of the investigator, affect assessments of clinical status to a significant degree.
- Subject is scheduled for elective or emergency surgery (excluding minor skin procedures under local or no anesthesia); timing of study drug pausing should be determined in consultation with the Gilead medical monitor.
- Any subject who develops a new infection during the study should undergo prompt and complete diagnostic testing appropriate for an immunocompromised individual, and the subject should be closely monitored.

NOTE: During the time of study drug interruption for any of the above, the subject may continue to have study visits and to take part in procedures and assessments, if deemed medically appropriate by the investigator.

3.5.2. Study drug discontinuation considerations:

The Gilead Medical Monitor should be consulted prior to study drug discontinuation when medically feasible.

Study medication should be permanently discontinued in the following instances:

- Any opportunistic infection
- Any **serious** infection that requires antimicrobial therapy or hospitalization, or any infection that meets SAE reporting criteria.
- Complicated herpes zoster infection (with multi-dermatomal, disseminated, ophthalmic, or CNS involvement)
- Evidence of active HCV during the study, as evidenced by HCV RNA positivity
- Evidence of active HBV during the study, as evidenced by HBV DNA positivity

- Unacceptable toxicity, or toxicity that, in the judgment of the investigator, compromises the subject's ability to continue study-specific procedures or is considered to not be in the subject's best interest
- Non-responder at Week 14 OR at 2 consecutive visits after Week 30 as outlined in Section 3.2
- Subject request to discontinue for any reason
- Subject noncompliance
- Pregnancy during the study (Section 7.7.2.1 and Appendix 5)
- Discontinuation of the study at the request of Gilead, a regulatory agency or an institutional review board or independent ethics committee (IRB/IEC)

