7.2.2. Assessment of Severity

The severity of AEs will be graded using the modified CTCAE, version 4.03. For each episode, the highest grade attained should be reported.

If a CTCAE criterion does not exist, the investigator should use the grade or adjectives: Grade 1 (mild), Grade 2 (moderate), Grade 3 (severe), Grade 4 (life-threatening) or Grade 5 (fatal) to describe the maximum intensity of the adverse event. For purposes of consistency with the CTCAE, these intensity grades are defined in [Table 7-1](#) and [Appendix 4](#).

Table 7-1. Grading of Adverse Event Severity

Grade	Adjective	Description
Grade 1	Mild	Asymptomatic or mild symptoms; clinical or diagnostic observations only; intervention not indicated
Grade 2	Moderate	Local or noninvasive intervention indicated; limiting age-appropriate instrumental ADL
Grade 3	Severe	Severe or medically significant but not immediately life-threatening; hospitalization or prolongation of hospitalization indicated; disabling; limiting self-care ADL
Grade 4	Life-threatening	Urgent intervention indicated
Grade 5	Death	Death related AE

* Activities of Daily Living (ADL) Instrumental ADL refer to opening preparing meals, shopping for groceries or clothes, using the telephone, managing money, etc.

** Self-care ADL refer to bathing, dressing and undressing, feeding self, using the toilet, taking medications, and not bedridden.

7.3. Investigator Requirements and Instructions for Reporting Adverse Events and Serious Adverse Events to Gilead

Requirements for collection prior to study drug initiation:

After informed consent, but prior to initiation of study medication, the following types of events should be reported on the case report form (CRF/eCRF): all SAEs and adverse events related to protocol-mandated procedures.

Adverse Events

Following initiation of study medication, collect all AEs, regardless of cause or relationship, until 30-days after last administration of study drug(s) must be reported to the CRF/eCRF database as instructed.

All AEs should be followed up until resolution or until the adverse event is stable, if possible. Gilead Sciences may request that certain AEs be followed beyond the protocol defined follow up period.

Serious Adverse Events

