For AEs associated with laboratory abnormalities, the event should be graded on the basis of the clinical severity in the context of the underlying conditions; this may or may not be in agreement with the grading of the laboratory abnormality.

All clinical and clinically significant laboratory toxicities will be managed according to uniform guidelines detailed in [Appendix 3](#) and as outlined below.

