7.5.2. Grades 3 Laboratory Abnormality or Clinical Event

- For Grade 3 clinically significant laboratory abnormality or clinical event, investigational medicinal product may be continued if the event is considered to be unrelated to investigational medicinal product.
- For a Grade 3 clinical event, or clinically significant laboratory abnormality confirmed by repeat testing, that is considered to be related to investigational medicinal product, investigational medicinal product should be withheld until the toxicity returns to \leq Grade 2.
- If a laboratory abnormality recurs to \geq Grade 3 following re-challenge with investigational medicinal product and is considered related to investigational medicinal product, then investigational medicinal product should be permanently discontinued and the subject managed according to local clinical practice. Recurrence of laboratory abnormalities considered unrelated to investigational medicinal product may not require permanent discontinuation.

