7.5.3. Grades 4 Laboratory Abnormality or Clinical Event

- For a Grade 4 clinical event or clinically significant Grade 4 laboratory abnormality confirmed by repeat testing that is considered related to investigational medicinal product, investigational medicinal product should be permanently discontinued and the subject managed according to local clinical practice. The subject should be followed as clinically indicated until the laboratory abnormality returns to baseline or is otherwise explained,

whichever occurs first. A clinically significant Grade 4 laboratory abnormality that is not confirmed by repeat testing should be managed according to the algorithm for the new toxicity grade.

Investigational medicinal product may be continued without dose interruption for a clinically non-significant Grade 4 laboratory abnormality (eg, Grade 4 CK after strenuous exercise or triglyceride elevation that is nonfasting or that can be medically managed) or a clinical event considered unrelated to investigational medicinal product.

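### For the same serious infection, Protocol 3.5.2 stops study drug permanently while 7.5.1 to 7.5.3 can allow it to continue or only withhold it, and the readable text states no precedence

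*Protocol*

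**What the plan says.** Protocol Section 3.5.2 opens its list with "Study medication should be permanently discontinued in the following instances". The list includes any serious "infection that requires antimicrobial therapy or hospitalization, or any infection that meets SAE reporting criteria". Neither severity grade nor relationship to study drug enters this criterion. Section 1.5, in its discussion of adalimumab risk, repeats the position: "Study drug will be discontinued for serious infections as outlined in section 3.5".

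Section 7.5 then sets general rules: "All clinical and clinically significant laboratory toxicities will be managed according to uniform guidelines detailed in" Appendix 3 and in the subsections that follow.

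- **7.5.1, Grades 1 and 2:** continuation is left to the investigator.
- **7.5.2, Grade 3, unrelated:** "investigational medicinal product may be continued if the event is considered to be unrelated to investigational medicinal product".
- **7.5.2, Grade 3, related:** "investigational medicinal product should be withheld until the toxicity returns to" Grade 2 or lower. Permanent discontinuation appears in this subsection only for a related laboratory abnormality that recurs on re-challenge.
- **7.5.3, Grade 4, related:** permanent discontinuation.
- **7.5.3, Grade 4, unrelated:** dosing may go on uninterrupted for "a clinical event considered unrelated to investigational medicinal product".

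Section 7.6 has the medical monitor discuss treatment-emergent toxicities with the investigator and decide what to do.

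**The concern.** Section 3.5.2 is triggered by seriousness. Section 7.5 is triggered by grade and causality. One infection can satisfy both, and the two then lead to different actions on study drug. An investigator who works from Section 7 when the event occurs could keep a subject on drug, or restart it, although 3.5.2 and 1.5 say drug is to stop.

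The first stake is safety. Section 1.5 reports that infections, including serious and fatal ones, were more common with filgotinib in the RA studies, and it describes serious infection as a risk of adalimumab.

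The second stake is the analysis. Under the SAP's primary (composite) estimand in Section 6.1, data after study drug discontinuation are treated as missing, and a missing binary response counts as non-response. SAP Section 3.8.2 runs the on-treatment period to the last dose of any study drug plus 7 days. Later efficacy data are therefore kept for a subject whose drug is withheld and restarted, but not for a subject who is stopped permanently. The choice of rule can thus change what counts in the primary efficacy dataset.

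**Working it through.** No sample size, power or error rate is involved, so the check sets the provisions side by side.

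**Step 1: can one event meet both rules?** Section 7.1.2 makes in-patient hospitalization a criterion for a serious adverse event. Table 7-1 in Section 7.2.2 places an event with "hospitalization or prolongation of hospitalization indicated" in Grade 3. Appendix 4 grades upper respiratory infection on the same scale and puts the need for intravenous anti-infective treatment at Grade 3. A hospitalized infection that is not immediately life-threatening therefore meets 3.5.2 and is also a Grade 3 clinical event under 7.5.2.

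**Step 2: compare the actions.** For every row, 3.5.2 gives permanent discontinuation.

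| Infection meeting 3.5.2 | Action under Section 7 | Same as 3.5.2? |
|---|---|---|
| Grade 1 or 2 | Continue at investigator discretion (7.5.1) | No |
| Grade 3, unrelated | May continue (7.5.2) | No |
| Grade 3, related | Withhold until Grade 2 or lower (7.5.2) | No |
| Grade 4, unrelated | May continue without interruption (7.5.3) | No |
| Grade 4, related | Permanent discontinuation (7.5.3) | Yes |

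The actions differ in 4 of 5 rows, but not equally. In three rows Section 7 permits what 3.5.2 rules out, so a site that stops drug breaches neither section. In the related Grade 3 row, Section 7 directs a different action. The Grade 1 or 2 row is an edge case: it needs an infection that is serious but graded low.

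**Step 3: look for a tie-break.** Section 3.5.2 refers to Section 7.7.2.1 for pregnancy but has no reference to 7.5 for infections. Section 7.5 refers to Appendix 3 and has no reference to 3.5.2. Section 7.6 cites Appendix 3, 7.5.2 and 7.5.3, but only for Grade 3 or 4 clinically significant laboratory abnormalities. Section 1.5 points to 3.5 without mentioning Section 7. None of these passages says which rule prevails.

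**Step 4: laboratory criteria.** The 3.5.2 laboratory stops (neutrophils, platelets, liver tests, creatinine clearance) carry no causality condition, whereas 7.5.2 and 7.5.3 make the action on clinically significant abnormalities depend on it. Section 6.7.4 narrows this gap: for laboratory results that may lead to discontinuation it asks for a prompt retest and refers to 3.5. The CTCAE limits are not reproduced in the protocol, so the documents establish the causality mismatch but not which 3.5.2 threshold falls in which grade.

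**The case against.** The strongest defence is that a specific rule overrides a general one. Section 7.5.2 never mentions infection, 3.5.2 does, and 1.5 restates the stop with a direct pointer to 3.5. That is good evidence of intent. It does not settle the matter, because 7.5 claims all clinical toxicities and uniform management, and nothing in the readable text ranks the sections.

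The second defence is central oversight. Section 3.5.1 asks for discussion with the medical monitor before dosing resumes, 3.5.2 asks for consultation before discontinuation when feasible, 7.6 gives the monitor a deciding role, and Section 7.3 requires SAE data to be sent to the sponsor within 24 hours. These steps reduce the chance of inconsistent handling. They do not remove it, since the monitor works from the same text.

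The third is that the content of Appendix 3 did not come through in the text reviewed, so an infection exception there cannot be excluded. This stands as a limit. However, 7.5 also directs management by the subsections below it, and those contain no exception.

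Three stronger readings are tempting and not supported:

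- **Sites do handle such events differently.** The documents offer no evidence of it; they show only that the text allows it.
- **Infection is the most important risk.** The protocol does not rank its risks, and Section 1.5 also names testicular and embryofetal findings.
- **The number of affected subjects can be projected from Phase 2b.** Section 1.2.3 reports that all 6 serious infections in CL-203 led to stopping, and that 2 serious infections did so in CL-204, where 4 subjects had serious infections. Those studies' stopping rules and the grade and causality of these infections are not given. Related Grade 4 events would not conflict, and a fatal event raises no question of continuing.

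**Conclusion.** The inconsistency is real and lies in the text. An infection that meets 3.5.2 can also fall under 7.5.1 to 7.5.3, and the study-drug action differs in four of five grade-by-causality combinations. They agree only for a related Grade 4 event. The core of the problem is the Grade 3 event and the unrelated Grade 4 event. A site following 7.5.2 or 7.5.3 as written could keep or restart drug in a subject for whom 3.5.2 and 1.5 call for discontinuation.

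The conclusion rests on infections being graded on the common scale, which Appendix 4 supports, and on Appendix 3 containing no exception, which could not be checked. The laboratory part is weaker: a causality mismatch, partly mitigated by 6.7.4. The number of subjects affected and any effect on efficacy estimates cannot be derived from the documents. The case for correction is that the passages concern stopping drug after a serious infection and give different actions for the same event.

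**What to change.** Check Appendix 3 first for an existing exception. Then reconcile 3.5.2 with 7.5.1, 7.5.2, 7.5.3, 7.6 and Appendix 3:

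- Add one sentence at the head of 7.5 stating which section governs when an event meets a 3.5.2 criterion.
- Put the matching cross-reference in 3.5.2.
- State whether causality plays any part for the 3.5.2 infections and for the 3.5.2 laboratory criteria, and keep 6.7.4 consistent with the answer.

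Which rule applies is for the sponsor to decide. The cost is a short protocol clarification and a letter to sites, with no new procedures, data or subjects.

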3.6. End of Study

End of Study is defined as when the last subject has completed 52 weeks of dosing plus the 4 week post treatment visit or has entered the LTE.

3.7. Post Study Care

All subjects who meet criteria for clinical response (per protocol), and who complete 52 weeks of study assessments will be offered an opportunity to participate in a LTE study (GS-US-417-0304). Subjects who discontinue early from the main study, or switch to standard of care treatment during the study, are not eligible for the LTE. The long term care of subjects who do not qualify or choose not to participate in the LTE will remain the responsibility of their primary treating physician.

3.8. Biomarker Samples

3.8.1. Biomarker Samples to Address the Study Objectives

The following biological specimens will be collected in this study which may be used to evaluate the association of exploratory systemic and/or tissue specific biomarkers with study drug response, including efficacy and/or adverse events and to help inform the mechanism of action and mechanism of intrinsic and acquired resistance to filgotinib in rheumatoid arthritis. The specific samples to be collected from all subjects (unless otherwise stated) include the following:

- Plasma, serum, and urine samples for potential analysis of circulating factors including but not limited to cytokines, metabolome, biomarkers of joint damage, and miRNA
- Paxgene blood samples for potential expression analyses
- Baseline blood cell pellets to assess host genetic association to clinical safety, efficacy and disease progression in CCI
- Whole blood samples for potential B-/T-cell receptor sequencing
- Vially frozen PBMCs (vfPBMCs) and Leukocyte subsets to profile immune cell subsets and inflammatory signaling pathways

The biomarker sample collection schedule is described in the Study Procedures Table ([Appendix 2](#)). Since biomarker science is a rapidly evolving area of investigation, it is not possible to prospectively specify all tests that may be performed on the specimens collected. The testing outlined above is based upon the current state of scientific knowledge. It may be modified during or after the end of the study to remove tests no longer indicated and/or to add new tests based upon the growing state of art knowledge. Any future testing of new parameters not described above must be approved by local authorities as applicable according to specific local regulations.

The biomarker samples will be destroyed no later than 15 years after the end of study unless the subject gives specific consent for the remainder of the samples to be stored for optional future research.

For sampling procedures, storage conditions, and shipment instructions, see the Sample Handling and Logistics Manual.

3.8.2. Biomarker Samples for Optional Future Research

CCI
[Redacted]

[Redacted]

[Redacted]

[Redacted]

CCI [Redacted]

[Redacted]

3.8.3. Biomarker Samples for Optional Genomic Research

CCI [Redacted]

[Redacted]

[Redacted]

[Redacted]

[Redacted]

3.9. **CCI** [REDACTED]

[REDACTED]

[REDACTED]

3.10. **CCI** [REDACTED]

[REDACTED]

[REDACTED]

4. SUBJECT POPULATION

4.1. Number of Subjects and Subject Selection

A sufficient number of subjects will be screened to ensure that approximately 1650 subjects with moderately to severely active RA will be randomized to one of 4 dosing groups.

4.2. Inclusion Criteria

Subjects must meet all of the following inclusion criteria to be eligible for participation in this study.

- 1) Male or female subjects who are ≥ 18 years of age, on the day of signing informed consent.
- 2) Have a diagnosis of RA (2010 ACR/EULAR criteria for RA) ([Appendix 8](#)), and are ACR functional class I-III .
- 3) Have ≥ 6 swollen joints (from a SJC66) and ≥ 6 tender joints (from a TJC68) at both Screening and Day 1 (need not be the same joints) ([Appendix 7](#)).
- 4) Must meet at least one of the following parameters at Screening:
 - a) ≥ 1 documented joint erosion on radiographs of the hands, wrists or feet by central reading AND positive result for anti-CCP Ab or RF (based on central laboratory),
OR
 - b) ≥ 3 documented erosions on radiographs of the hands, wrists or feet by central reading if both antibodies (ie, RF, anti-CCP) are negative (based on central laboratory),
OR
 - c) Serum CRP ≥ 6 mg/L (based on central laboratory)
- 5) Ongoing treatment with a stable dose of MTX as described below:
 - a) Use of oral MTX on a continuous basis for at least 12 weeks prior to Day 1 and on a stably prescribed dose of 7.5-25 mg/weekly for at least 4 weeks prior to Day 1. Stable doses of < 7.5 mg/week are allowed only in the presence of intolerance or toxicity to higher doses or where higher doses are prohibited by the local label or local clinical practice. Doses > 25 mg weekly are not permitted during the study.
 - b) Subjects should be receiving an adequate and prescribed stable dose of folic acid (≥ 5 mg/week total dose or as per local clinical practice) which should be confirmed or initiated at Screening, and continued throughout the study.

- c) Subjects may use concomitant hydroxychloroquine (HCQ) ≤ 400 mg/day or chloroquine ≤ 250 mg/day during the study with the prescription having been stable for at least 4 weeks prior to Day 1.
- 6) Females of childbearing potential (as defined in [Appendix 5](#)) must have a negative pregnancy test at screening and Day 1
- 7) Male subjects and female subjects of childbearing potential who engage in heterosexual intercourse must agree to use protocol specified method(s) of contraception as described in [Appendix 5](#).
- 8) Lactating female subjects must agree to discontinue nursing from Screening through the end of their study participation.
- 9) Meet one of the following tuberculosis (TB) Screening criteria:
 - a) No evidence of active or latent TB:
 - o A negative QuantiFERON[®] TB-Gold In-Tube test at Screening and
 - o A chest radiograph (views as per local guidelines) taken at Screening or within the 3 months prior to Screening (with the report or films available for investigator review) without evidence of active or latent TB infection and
 - o No history of either untreated or inadequately treated latent or active TB infection
 - b) Previously treated for TB: ie, if a subject has previously received an adequate course of therapy as per local standard of care for either latent TB (9 months of isoniazid in a location where rates of primary multi-drug resistant TB infections are $< 5\%$ or an acceptable alternative regimen) or active TB (acceptable multi-drug regimen). In these cases, no QuantiFERON[®] TB-Gold In-Tube test (or equivalent assay) need be obtained, but a chest radiograph must be obtained if not done so within 3 months prior to Screening (with the report or films available for investigator review). It is the responsibility of the investigator to verify the adequacy of previous anti-tuberculosis treatment and provide appropriate documentation.
 - c) Newly identified latent TB during Screening: ie, a subject who has a newly identified positive diagnostic TB test result (defined as a positive QuantiFERON[®] TB Gold in Tube test [or equivalent assay]) in which active TB has been ruled out and for which appropriate, ongoing, prophylactic treatment for latent tuberculosis has been initiated prior to the first administration of study medication. Adequate treatment for latent TB is defined according to local country guidelines for immunocompromised subjects.

Cases falling under category “b” and “c” need to be approved by the Sponsor prior to enrollment in the study. No subject with currently ACTIVE TB may be enrolled in the study, regardless of past or present anti-TB medication use.

- 10) Able and willing to sign the informed consent as approved by the Independent Ethics Committee (IEC)/Institutional Review Board (IRB). Written consent must be provided before initiating any screening evaluations. Subjects must have read and understood the informed consent form (ICF), must fully understand the requirements of the study, and must be willing to comply with all study visits and assessments; subjects who cannot read or understand the ICF may not be enrolled by a guardian or any other individual.
- 11) Able and willing to perform subcutaneous self-injections or have a caregiver able, willing and available to administer the injections.
- 12) Subjects receiving non-prohibited medication for any reason should be on a stable dose (defined as no change in prescription) within 7 days or 5 half-lives (whichever is longer) prior to the first administration of study drug on Day 1.

